Sample: Data will be collected for sites A-E, with two control Trusts per intervention Trust, matched on comparable outcomes pre-intervention. Contextual factors in the QualDash program theory may be used as additional matching criteria. A CITS study requires data for a minimum of three time points pre-intervention and three time points postintervention and must also allow for any seasonal effect on the outcomes. 106 Therefore, monthly data will be obtained for 24 months pre-intervention and 12 months post-intervention. For MINAP, Cumulative Missed Opportunities for Care (CMOC) will be used as the primary process measure (described below). The average CMOC for patients on a ward will be averaged for each month, so that there are 36 observations clustered within each of 15 hospitals. Taking the intra-class correlation to be 0.15, this yields a design effect of 6.25. Hence the effective number of observations is 15*36/6.25=86.4. Using Cohen's approach to sample size calculation this means that an effect size of 0.17 can be estimated with 80% given that there are six parameters in the model (including the coefficient for QualDash). Converting this to the percentage of variation that can be explained by the model, this yields 20.5%. Translating this back to CMOC, currently 49.6% are discharged from hospital without missing any of the nine opportunities for care, and we would be powered at the 80% level to detect an improvement from an average of 8.33 opportunities achieved to 8.46. Thus our study has good power to detect small but meaningful clinical improvements. For PICANet, the primary process measure will be the use of non-invasive ventilation first for patients requiring ventilation, 10% of the admitted population. 107 On average there are 5.25 ventilation cases per month per hospital. With a further design effect from patients clustered within hospitals, based on the reported ICC=0.065 giving DEff=1.276, the actual anticipated number of patients is 1701 giving an effective number of 213: 71 exposed to QualDash and 142 controls. This yields 80% power to detect a change from 32% to 53% which is a feasible target given that the use of non-invasive ventilation first will be highlighted by QualDash.

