Data collection: For MINAP, the primary outcome will be the composite process measure CMOC. This has nine components (pre-hospital ECG, acute use of aspirin, timely perfusion, prescription at hospital discharge of aspirin, thienopyridine inhibitor, ACE-inhibitor, HMG-CoA reductase inhibitor, beta blocker, referral for cardiac rehabilitation) and, in previous work by members of the team, CMOC has been shown to be associated with mortality. ¹⁰⁸ For PICANet, the primary outcome will be use of non-invasive ventilation first for patients requiring ventilation, which has been shown to be associated with reduced mortality. ¹⁰⁷ Secondary outcomes will be determined on the basis of findings from Phase 1 regarding interviewees' perceptions of the value of particular measures and the extent to which they can be impacted by QI initiatives and through consultation with our LAG.

Analysis: Monthly MINAP and PICANet data will be extracted to spreadsheets for analysis with R software. ¹⁰⁹ For each intervention Trust, there will be 72 data points prior to introduction (24 for the intervention Trust and 48 for the control Trusts) and 36 data points post intervention (12 for the intervention Trust and 24 for the control Trusts). For both NCAs, the outcome will be regressed upon time and the intervention (QualDash). The time component will include a seasonal effect (quarterly effect) and will allow for a (linear) time trend. To account for clustering of monthly observations within hospitals a random intercept will be fitted, although a fixed effect for hospital as a sensitivity analysis will be explored. Although the intervention is abrupt, its impact may well be 'phased in' over a few months, perhaps three. The timing of the bedding in of the intervention will be reported from the multi-site case study. Then a partial effect can be considered for this period with the interaction effect stepping up in a linear fashion.

4b. Multi-site case study

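### The 6.25 design effect is for an exposure that never changes within a hospital; QualDash switches on within hospitals, so the effective sizes of 86.4 and 213 do not describe the planned analysis

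*Protocol*

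**What the plan says.** All of this is in the protocol, Phase 4, section 4a.

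Under Sample, the MINAP measure is averaged by month, "so that there are 36 observations clustered within each of 15 hospitals". Then: "Taking the intra-class correlation to be 0.15, this yields a design effect of 6.25", and "Hence the effective number of observations is 15*36/6.25=86.4". From that number, Cohen's method gives the statement that "an effect size of 0.17 can be estimated with 80% given that there are six parameters in the model", which is carried on to a detectable CMOC improvement from 8.33 to 8.46. For PICANet a further design effect of 1.276 is applied, and 1701 ventilated patients become an effective 213, said to give 80% power for a change from 32% to 53%.

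The same paragraph fixes the design: "monthly data will be obtained for 24 months pre-intervention and 12 months post-intervention", with "two control Trusts per intervention Trust, matched on comparable outcomes pre-intervention". Under Analysis, the outcome is regressed on time (linear trend and quarterly effects) and on QualDash, and for clustering "a random intercept will be fitted, although a fixed effect for hospital as a sensitivity analysis will be explored".

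**The concern.** The factor 1+(m-1)×ICC says how much variance grows when a comparison is made between whole clusters, that is, when every observation in a cluster has the same exposure. That is a parallel cluster comparison. Here the exposure is off for 24 months and on for 12 in the same hospital. A stable difference between hospitals is common to both periods, so most of it drops out of the QualDash coefficient once a hospital intercept is in the model. What chiefly inflates the variance of a within-hospital contrast is month-to-month correlation beyond the hospital intercept, and the calculation has no term for it.

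The 6.25 enters the power statement for both primary outcomes. The protocol concludes from it that power is good for small but meaningful improvements, and a null result would be read against those figures.

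**Working it through.** **1. Reproducing the plan's figures**

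- Design effect: 1 + 35×0.15 = 6.25. MINAP: 15×36 = 540 and 540/6.25 = 86.4.
- PICANet: 9 hospitals (sites A-C plus two controls each) × 36 × 5.25 = 1701. Further design effect: 1 + 4.25×0.065 = 1.276. Then 1701/(6.25×1.276) = 213.
- With an effective 86.4, six parameters, 80% power and 5% significance (assumed, not stated), the detectable effect is f² = 0.1705, the stated 0.17.

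Everything reproduces, so this is a choice of formula and not a slip in arithmetic.

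**2. Which design 6.25 belongs to**

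I took the generalised least squares variance of the QualDash coefficient (intercept, linear month, three quarter terms, QualDash) at ICC 0.15 and divided it by the variance under independence. If the intervention hospitals are treated as exposed in all 36 months, the ratio is exactly 6.25.

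**3. The planned switch-on, by hand**

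Set the total variance of a monthly value to 1, so 0.15 is between hospitals and 0.85 within. Include a common post-period term. The time effects are shared by all hospitals, so the coefficient compares post-period means adjusted for pre-period means.

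- Variance of a hospital's pre-period mean: 0.15 + 0.85/24 = 0.18542
- Variance of its post-period mean: 0.15 + 0.85/12 = 0.22083
- Covariance of the two: 0.15
- Post-period variance given the pre-period mean: 0.22083 - 0.15²/0.18542 = 0.09949
- QualDash coefficient, 5 v 10 hospitals: 0.09949×(1/5 + 1/10) = 0.02985
- Under independence: 1/(5×12) + 1/(10×12) = 0.02500
- Inflation: 0.02985/0.02500 = **1.19**

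The 3 v 6 PICANet layout gives the same ratio (0.04974/0.04167). Without the common post-period term, the full matrix calculation gives 0.02304×1.157, an inflation of **1.16**. With hospital as a fixed effect (the planned sensitivity analysis) and the post-period term, it is 0.85×(1/12 + 1/24)×(1/5 + 1/10)/0.025 = 1.28.

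**4. Adding residual autocorrelation (assumed; the protocol gives none)**

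ICC 0.15, random intercept, AR(1) residual:

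| AR(1) | no post term | post term |
|---|---|---|
| 0 | 1.16 | 1.19 |
| 0.2 | 1.60 | 1.66 |
| 0.4 | 2.15 | 2.24 |
| 0.6 | 2.68 | 2.85 |
| 0.7 | 2.76 | 3.00 |
| 0.8 | 2.46 | 2.76 |

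The inflation peaks near 0.7 and then falls (1.53 at 0.9 without the post term). With no autocorrelation and no post term, changing the ICC to 0.05 or 0.30 gives 1.19 or 0.98.

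**5. What this does to a detectable difference**

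At 80% power and 5% two-sided, the detectable level change is 2.80 × the standard error. For MINAP with the post term, that is 2.80×√0.02985 = 0.48 standard deviations of a monthly mean. Using 6.25 instead gives 2.80×√(6.25×0.025) = 1.11. Without the post term the pair is 0.46 and 1.06.

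**The case against.** The strongest reply is that the error is on the safe side and changes little. The five sites were chosen purposively, controls are matched two to one, and the outcomes are routine audit data. Nothing shows that 6.25 set the number of sites, and the analysis itself is unaffected. The Study Steering Committee, which is to include an expert in this design, reviews the Phase 4 evaluation at the end of Phase 3. All of this stands, and it limits the consequence. It does not make the stated figures describe the planned analysis.

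Four stronger readings are tempting and should not be drawn.

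- *The study is underpowered, or the stated power could err either way on this account.* Every inflation tried lies below 6.25. That includes structures outside the plan in which the hospital level is partly or wholly redrawn between periods; these gave larger inflation than the table but still less than 6.25. The PICANet split of 71 exposed to 142 controls does work the other way. It is the 1:2 hospital ratio, although only 12/36×1/3 = 1/9 of patients (189 of 1701) are exposed. That is a separate matter and lends no support here.
- *The future cluster trial will be mis-sized.* The protocol uses the time series results for the trial's effect size, choice of audits, outcome variability and intervention length. It does not plan to reuse 6.25.
- *The correct effective number is 540/1.157 = 467.* That ratio concerns one coefficient. The protocol puts its number into a six-parameter calculation, so the two are not interchangeable.
- *The plan omits an AR(1) term it had promised.* It promises none, and residual structure may properly be left to an analysis plan not shown here.

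**Conclusion.** The point holds as a mismatch between the sample size formula and the design and model given in the same section. At the stated ICC of 0.15, the variance inflation for the QualDash coefficient is about 1.16 to 1.19 under the planned random intercept, and about 1.6 to 3.0 if AR(1) of 0.2 to 0.8 is assumed. The protocol uses 6.25. The effective sizes of 86.4 and 213, and the power and detectable effects derived from them, therefore do not belong to the planned analysis. Taken alone, the error understates the information available.

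The result rests on an exchangeable hospital effect, a level change at month 25, equal monthly weights, and a linear approximation for the PICANet proportion. The exact inflation depends on a correlation structure that the protocol does not give; the direction did not change in any case tried.

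**What to change.** Drop the 6.25 step for both MINAP and PICANet. Compute power, or the detectable effect, for the single QualDash coefficient from the model under Analysis: random hospital intercept, linear trend, quarterly effects, and exposure in the 12 post-intervention months of the intervention hospitals only. Estimate the ICC from the audit data that the protocol says are already held. Show the result over a short range of residual autocorrelation, labelled as an assumption. Then restate the MINAP and PICANet detectable effects from that calculation.

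The cost is a short recalculation and revised wording. Sites, data collection and analysis stay as they are.

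### The detectable effect for the MINAP primary outcome (CMOC) lacks a valid derivation: 0.17 converts to 14.5% of variation, not 20.5%, and the move to 8.46 opportunities has no stated basis

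*Protocol*

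**What the plan says.** The calculation is in the protocol, Phase 4, section 4a (Controlled interrupted time series study), under Sample. Monthly hospital means of CMOC are the unit, "so that there are 36 observations clustered within each of 15 hospitals". Clustering is handled by a design effect: "Taking the intra-class correlation to be 0.15, this yields a design effect of 6.25". Then "Hence the effective number of observations is 15*36/6.25=86.4".

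From this the protocol concludes that "an effect size of 0.17 can be estimated with 80% given that there are six parameters in the model", the six including the coefficient for QualDash. The next sentence reads "Converting this to the percentage of variation that can be explained by the model, this yields 20.5" per cent. Finally, noting that 49.6% of patients currently miss none of the nine opportunities, it says the study has 80% power "to detect an improvement from an average of 8.33 opportunities achieved to 8.46", and describes this as good power for small but clinically meaningful gains.

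No alpha is stated for this calculation, the effect-size measure is not named, no standard deviation of monthly CMOC is given, and the formula for the last step is not shown. Under Analysis, the same section plans a regression on QualDash, a linear trend and quarterly season, with a random intercept for hospital.

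**The concern.** The chain has three links after the effective sample size: an effect size, a percentage of variation, and a change in mean CMOC. The first conversion gives a percentage larger than the effect size it started from, which cannot happen when f² is turned into R². The effect size is tied to the number of parameters in the model, which suggests an overall test and not a test of QualDash. The last link turns a share of variance into a difference in means without a standard deviation.

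The 0.13 gain is the only detectable effect stated for this outcome, so it is the natural yardstick for a null result. The protocol's summary says that the interrupted time series results will set the effect size for a future cluster trial, and Phase 5 says that they will be considered in deciding whether such a trial is justified. If 0.13 is not properly derived, a null result could be wrongly read as having had 80% power against a gain of that size.

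**Working it through.** **Inputs, all from section 4a:** 15 hospitals, 36 months, ICC 0.15, six parameters, effect size 0.17, 80% power, 20.5%, nine opportunities, 49.6% with none missed, 8.33 and 8.46. **Assumed:** alpha 0.05.

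**1. Effective sample size.** Design effect = 1 + 35 × 0.15 = 6.25; 540/6.25 = 86.4. Both reproduce.

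**2. What 0.17 is.** In Cohen's regression F test the noncentrality is f² × (u + v + 1), with u numerator and v denominator degrees of freedom. For 80% power:

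| u | v | f² needed | Power at f² = 0.17 |
|---|---|---|---|
| 6 | 79.4 | 0.1705 | 0.799 |
| 6 | 80.4 | 0.168 | 0.804 |
| 5 | 80.4 | 0.159 | 0.830 |
| 1 | 79.4 | 0.099 | 0.957 |
| 1 | 84.4 | 0.093 | 0.966 |

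So 0.17 is f² for a joint test of all six terms. Five degrees of freedom gives about 0.16, and one gives about 0.09 to 0.10.

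**3. Conversion to variation explained.** R² = f²/(1 + f²) = 0.17/1.17 = 0.145. The stated figure is 0.17/(1 − 0.17) = 0.205, which is the formula for going from R² to f².

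The alternative reading, that 0.17 is R² and 20.5% is f², does not fit. Power at f² = 0.205 with u = 6 is about 0.88, not 0.80, and the text calls 20.5% the variation explained.

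**4. The step to 8.46.** The protocol does not show it. One reconstruction matches both ends:
- If the nine opportunities are independent and equally likely to be met, each is met with probability 0.496^(1/9) = 0.925. The mean is 9 × 0.925 = 8.325, the stated 8.33, leaving 0.675 missed.
- Cutting 0.675 by 20.5% gives 9 − 0.675 × 0.795 = 8.464, the stated 8.46.
- The same step with 14.5% gives 9 − 0.675 × 0.855 = 8.42.

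This would treat R² as a relative reduction in missed opportunities, which it is not.

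**5. What a valid step would need.** For one coefficient, step in residual SDs = √(f² / variance of the exposure indicator). Exposed hospital-months are 5 × 12 = 60 of 540, so that variance is (1/9)(8/9) = 0.0988.
- On the protocol's 86.4 effective observations, with QualDash uncorrelated with the other terms: √(0.0988/0.0988) = 1.00 SD. Assumed SDs of 0.05, 0.10, 0.13, 0.20 and 0.30 then give detectable gains of about 0.05, 0.10, 0.13, 0.20 and 0.30.
- If clustering is instead handled by removing hospital effects, with no design effect and no autocorrelation, the step is about 0.5 within-hospital SD.

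The answer therefore turns on an SD and a correlation structure that the protocol does not give, and it can fall on either side of 0.13.

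**The case against.** The strongest reply is that none of this makes the power claim false. The six-degree-of-freedom choice raises the f² required, and at f² = 0.17 a one-degree-of-freedom test has about 96% power. If clustering is counted once, through the hospital effect, the detectable gain could be 0.13 or less for plausible SDs. The number of sites, the two controls per site and the 24 + 12 months are not derived from this calculation. The eventual estimate and confidence interval do not depend on it, and the impact found in the time series is not a formal progression criterion. The route to 8.46 is also a reconstruction.

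Most of that stands. A reader might infer that the study is underpowered for CMOC, or that no result could be judged against its design. The protocol supports neither: without the SD the detectable change is unknown in both directions, and the confidence interval can be read on its own terms. What the reply does not rescue is the 20.5%, which is wrong under any reading that reproduces 80% power, or the 8.46, which has no stated basis.

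**Conclusion.** The point holds as an error of derivation. Variation explained is 14.5%, not 20.5%. The 0.17 is a whole-model figure and says nothing directly about QualDash, although this alone does not indicate low power. The change from 8.33 to 8.46 does not follow from a variance-explained figure when no SD of monthly hospital CMOC is given. If it came from cutting missed opportunities by 20.5%, the corrected percentage would give 8.42, but that route is inferred and would be invalid with either percentage.

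The arithmetic rests on alpha 0.05 and on reading 0.17 as f². The second is supported by the reproduction at six degrees of freedom and by the failure of the alternative. The conclusion is limited to this: the statement of good power for small clinical gains in CMOC has no valid derivation.

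**What to change.** Correct 20.5% to 14.5%, or delete the sentence. Replace the 8.33 to 8.46 statement with the change in mean CMOC detectable with 80% power for the single QualDash coefficient. State alpha, and take the SD and within-hospital correlation of monthly CMOC from MINAP data. Compute it for the planned random-intercept model, in closed form or by simulation, counting clustering once: through the model or through a design effect, not both.

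The cost is a recalculation and a wording change. The protocol says that MINAP data are already held at the University, and the steering committee is due to review the Phase 4 design at the end of Phase 3. No extra data collection is needed, and the planned analysis and progression criteria are unaffected.

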To ensure the study generates findings that are generalisable beyond a single NCA, we have chosen to work with two NCAs, MINAP and PICANet. MINAP and PICANet are delivered by different suppliers and involve different clinical specialties working with different patient groups, multiple professional groups (medical and nursing), and include multiple types of measures (structure, process, and outcome). They also differ in data quality and completeness. MINAP has been running continuously since 2000, delivered by the National Institute for Cardiovascular Outcomes Research, and data are contributed by all hospitals in England, Wales and Northern Ireland that admit patients with acute coronary syndromes. PICANet was set up in 2002 by the Universities of Leeds, Leicester and Sheffield and contains data from all NHS Paediatric Intensive Care Units (PICUs) in England and Wales.

There are three main funding arrangements for independent NCAs: subscription by NHS Trusts; funded by a charity or professional body; or funded by NHS England. To explore the impact of funding arrangements, in Phase 1 we will also gather data on the National Cardiac Arrest Audit (NCAA; funded by Trust subscription), the National Audit of Cardiac Rehabilitation (NACR; funded by the British Heart Foundation), and the Elective Surgery National PROMs Programme

(funded by NHS England). There are a number of independent surgery NCAs where participation is at the individual clinician, rather than Trust, level; to understand the impact of this difference, in Phase 1 we will gather data about the British Association of Urological Surgeons (BAUS) audits. In Phase 5, we will explore the applicability of QualDash to those independent NCAs where data is collected intermittently rather than continuously,

We will work with three NHS acute Trusts (sites A-C) that participate in both MINAP and PICANet. These Trusts have been selected to ensure variation in key outcome measures (MINAP: 30 day mortality for ST-elevation myocardial infarction (STEMI) patients; PICANet: risk adjusted standardised mortality ratio), as shown in Table 1.

Because Trusts that participate in PICANet tend to be larger and to be teaching hospitals, they are not representative of the range of Trusts that participate in MINAP. Therefore, MINAP use will also be studied in two district general hospitals (DGHs; sites D-E) that do not have a PICU. These have been selected to ensure variation in the same key MINAP measure.

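### The PICANet effective number of 213 and its 80% power rest on an ICC of unstated level, a design effect reused from MINAP, and a parallel-group calculation that is not the planned before/after model; the power is unsupported in either direction.

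*Protocol*

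**What the plan says.** All the figures are in the Protocol, Phase 4, section 4a (Sample), unless noted.

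- **MINAP.** "The average CMOC for patients on a ward will be averaged for each month, so that there are 36 observations clustered within each of 15" (the last figure is the number of MINAP sites and controls together). The clustering allowance for these monthly averages follows: "Taking the intra-class correlation to be 0.15, this yields a design effect of 6.25". This is 1 + (36 - 1) x 0.15.
- **PICANet volume.** "On average there are 5.25 ventilation cases per month per hospital".
- **PICANet clustering.** "With a further design effect from patients clustered within hospitals, based on the reported ICC=0.065 giving DEff=1.276". The text then gives 1701 actual patients and 213 effective ones, split into 71 exposed and 142 controls.
- **PICANet power.** "This yields 80% power to detect a change from 32% to 53" per cent.
- **Design.** "monthly data will be obtained for 24 months pre-intervention and 12 months post-intervention", "with two control Trusts per intervention Trust, matched on comparable outcomes pre-intervention". Under Setting/context: "We will work with three NHS acute Trusts (sites A-C) that participate in both MINAP and PICANet". PICANet therefore has 3 intervention and 6 control hospitals.
- **Analysis (section 4a, Analysis).** The outcome is regressed on time and the intervention, with a linear trend and a quarterly effect. A random intercept for hospital is fitted to the monthly data, and a fixed hospital effect is a sensitivity analysis.

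The section does not say that 6.25 is applied to PICANet. It gives no ICC for monthly non-invasive ventilation rates, and it does not say over what time span the 0.065 was estimated.

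**The concern.** Three features of the calculation do not fit together.

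1. The ICC is described as patients within hospitals, but the cluster size behind 1.276 is one hospital-month (5.25), not the hospital's full contribution over the study.
2. The second factor was set for another audit, another outcome and another patient group. No reason is given for applying it to non-invasive ventilation.
3. The calculation compares two parallel groups of effective patients and treats every month of the intervention hospitals as exposed. The planned analysis is a controlled before/after comparison within hospitals.

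This is the power statement for the PICANet primary outcome. Phase 5 uses the time series results when deciding whether a cluster trial is justified, which audits it should include and, according to the summary, what effect it should be powered to detect. If 80% is taken at face value, a null PICANet result could be read as evidence against an effect that the study may or may not have been able to find.

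**Working it through.** **Reproducing the plan's figure** (two-sided 5% assumed; the section does not state it)

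- Patients: 9 hospitals x 36 months x 5.25 = 1701.
- First factor: 1 + (5.25 - 1) x 0.065 = 1.276.
- Second factor: 1 + 35 x 0.15 = 6.25.
- Product: 6.25 x 1.276 = 7.98.
- Effective number: 1701/7.98 = 213, split 1:2 into 71 and 142.
- Power for 53% v 32% at 71 v 142 (normal approximation): 84%, or 80% with continuity correction.

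Every stated number reproduces, and the 213 confirms that the MINAP factor was reused. Table 1 supports the 5.25: 10% of the mean of 799, 318 and 769 patients a year, divided by 12, is 5.24.

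**Reading A: 0.065 is a constant ICC between any two patients of the same hospital, as worded**

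- Patients per hospital: 36 x 5.25 = 189.
- Design effect: 1 + 188 x 0.065 = 13.22.
- In two-stage form, the implied ICC of month means is 5.25 x 0.065/1.276 = 0.267. The months factor is 1 + 35 x 0.267 = 10.36, and 10.36 x 1.276 = 13.22 again.
- Effective number: 1701/13.22 = 129 (43 v 86).
- Power in the same two-proportion calculation: 63%, or 56% with continuity correction.
- The plan's 7.98 would match a constant hospital ICC of (7.98 - 1)/188 = 0.037.

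**Reading B: 0.065 is the ICC between patients of the same hospital in the same month**

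- A month-mean ICC of 0.15 then implies a between-month ICC of 0.15 x 1.276/5.25 = 0.036.
- The ratio to the same-month value is 0.036/0.065 = 0.56. That is a coherent pair, and 7.98 could stand as a two-stage factor, provided 0.15 is justified for this outcome.

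**Who is exposed**

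- The 71 is 3 x 36 x 5.25/7.98, so it includes the 24 pre-intervention months of sites A-C.
- Exposed patients are 3 x 12 x 5.25 = 189 actual, or 189/7.98 = 24 effective at the plan's own factor.

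**What the planned contrast depends on** (rough check by difference in differences on proportions; trend, season and phase-in ignored; equal hospital sizes; normal approximation)

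- Cells: intervention post 189 patients at 53%; intervention pre 378, control post 378 and control pre 756, all at 32%.
- Sampling variance: 0.53 x 0.47/189 + 0.32 x 0.68 x (1/378 + 1/378 + 1/756) = 0.00132 + 0.00144 = 0.00276, so the SE is 0.0525.
- With no hospital-by-period variation: 0.21/0.0525 = 4.00, and power is Phi(4.00 - 1.96) = 98%.
- Suppose hospitals differ in their before/after change with SD t. The variance gains t² x (1/3 + 1/6) = t²/2. Power is 80% when the SE is 0.21/2.80 = 0.075, that is t² = 2 x (0.00562 - 0.00276) = 0.0057, so t is about 0.076 (7.6 percentage points).
- At an assumed t of 5, 10 and 15 points, power is 91%, 66% and 43%. The documents give no value of t. Allowing for only nine hospitals (a t rather than a normal reference) would lower these figures.

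**The case against.** The strongest defence is that nothing has been miscalculated. All the PICANet figures reproduce, and the description of the factor as a further design effect signals a second stage on top of months within hospitals. Patients within hospital-month times months within hospital is a valid form, and the analysis does use monthly data. This stands: using 5.25 is not an error in itself.

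A reader might also infer that 0.15 and 0.065 contradict each other. They do so only if 0.065 holds unchanged over 36 months. The document calls the value reported without giving its time frame, so Reading B remains open. What survives is that the text names hospitals, not hospital-months, and offers no support for Reading B.

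The most tempting inference is that the study is underpowered, with 129 effective patients and 63% power. The documents do not support that. The 13.22 factor assumes a constant hospital effect and a parallel comparison. A hospital intercept largely removes constant hospital differences from a before/after contrast, and in that very case the rough check gives about 98%. Conversely, power figures below 80% for the planned contrast need an assumed amount of hospital-by-period variation for which the document gives no basis.

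**Conclusion.** The PICANet effective number of 213 and the 80% power are unsupported, though not arithmetically wrong. The level of the 0.065 ICC is unclear, and the wording used points to a factor of 13.2 rather than 7.98. The 6.25 is borrowed without comment from MINAP CMOC. The 71 counts pre-intervention months as exposed, when only 189 actual patients are.

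Within the plan's own two-proportion method, Reading A gives 129 effective patients and 63% power (56% with continuity correction), and Reading B could leave 213 standing if 0.15 were justified. Neither is the power of the planned analysis. For the before/after model with a hospital intercept, power could be well above 80% if hospital-by-period variation is negligible. It falls below 80% once hospitals differ in their change by more than about 7.6 percentage points (SD), on the simplifications listed in the working. The conclusion is therefore that the stated 80% is unsupported in either direction, not that the study is too small.

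**What to change.** In section 4a (Sample):

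1. State the level and time span of the 0.065 ICC (same hospital, or same hospital and month).
2. Remove the 6.25 x 1.276 factor from the PICANet calculation.
3. Recompute power or the detectable change from the planned model: 3 intervention and 6 control hospitals, 24 + 12 months, 5.25 cases a month, with only the 3 x 12 post-intervention months exposed. Do this over a stated range of hospital-by-period variance.
4. Replace the 213, the 71/142 split and the 80% with the result and its range. The 129 and 63% should not be put in their place.

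The cost is a recalculation and probably a wider stated range. No added sites, data or change to the analysis are needed.

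### The PICANet power statement counts 24 pre-launch months as exposed to QualDash, so its 80% does not follow from the plan's own inputs

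*Protocol*

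**What the plan says.** All of this is in the Protocol. Setting/context fixes the PICANet intervention sites: "We will work with three NHS acute Trusts (sites A-C) that participate in both MINAP and PICANet".

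Phase 4, 4a (Controlled interrupted time series study), Sample, adds controls "with two control Trusts per intervention Trust, matched on comparable outcomes pre-intervention" and sets the window: "monthly data will be obtained for 24 months pre-intervention and 12 months post-intervention". For PICANet it gives the volume, "On average there are 5.25 ventilation cases per month per hospital", a total of 1701 patients and a patient-level design effect of 1.276 from an ICC of 0.065. This is described as a further design effect, on top of the one derived for MINAP: "Taking the intra-class correlation to be 0.15, this yields a design effect of 6.25". The result is "giving an effective number of 213: 71 exposed to QualDash and 142 controls", and the conclusion is "This yields 80% power to detect a change from 32% to 53" per cent.

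Phase 4, 4a, Analysis, sets out the data points for each intervention Trust. There are 72 before introduction (24 of them from the intervention Trust) and "36 data points post intervention (12 for the intervention Trust and 24 for the control Trusts"). The planned model regresses the outcome on a linear time trend, a quarterly seasonal effect and QualDash, with a random intercept for hospital. A fixed hospital effect is a sensitivity analysis, and a phase-in of perhaps three months is allowed for.

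**The concern.** The 71 is labelled as exposed, but it is obtained by splitting the whole 36-month sample 1:2 by hospital. Two thirds of those patients were ventilated before QualDash existed in their hospital. The calculation treats a before-and-after design with controls as if the intervention hospitals had used QualDash from the first month.

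This sentence is the only quantitative support for the PICANet primary outcome. Phase 5 (Summary of method) keeps the time-series impact outside the formal progression criteria. It nevertheless says that impact will be considered when judging whether a cluster trial is justified, and that the time-series data will inform whether MINAP, PICANet or both enter it. A PICANet result, null or positive, would then be read against a power figure that does not describe the design.

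**Working it through.** **Inputs from the Protocol.** 3 intervention hospitals (Setting/context). 2 controls each, so 6 controls and 9 hospitals; 24 + 12 = 36 months; 5.25 cases per hospital-month; rates 32% and 53% (4a, Sample). Design effects: 1 + 35 x 0.15 = 6.25 and 1 + 4.25 x 0.065 = 1.276. Alpha and sidedness are not stated; two-sided 0.05 is assumed throughout.

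**Step 1: reproduce the plan's numbers.**
- 9 x 36 x 5.25 = 1701 patients.
- 1701 / (6.25 x 1.276) = 213.3.
- One third is 71.1 and two thirds is 142.2.

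Every stated count is recovered, so the split is by hospital over all 36 months.

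**Step 2: reproduce the plan's power.** For two proportions with n1 unexposed and n2 exposed, pooled rate p and d = 0.21:

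power = Φ{[d − c − 1.96 √(p(1−p)(1/n1 + 1/n2))] / √(0.32·0.68/n1 + 0.53·0.47/n2)},

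where c = ½(1/n1 + 1/n2) with continuity correction and 0 without.

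With 142 v 71: p = 0.39, null SE = 0.0709, alternative SE = 0.0710, c = 0.0106.
- With correction: (0.21 − 0.0106 − 0.1390)/0.0710 = 0.85, power 80.3%.
- Without correction: 84.2%.

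The stated 80% is recovered as a continuity-corrected two-group test on the 71/142 split.

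**Step 3: correct only the exposed count.**
- Patients in intervention hospitals: 3 x 36 x 5.25 = 567.
- Of these, after launch: 3 x 12 x 5.25 = 189.
- Unexposed: 1701 − 189 = 1512.
- Effective numbers on the plan's design effects: 189/7.975 = 23.7 and 1512/7.975 = 189.6.

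With 189.6 v 23.7: p = 0.343, null SE = 0.1035, alternative SE = 0.1080, c = 0.0237.
- With correction: (0.21 − 0.0237 − 0.2028)/0.1080 = −0.15, power 44%.
- Without correction: 53%.

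The rate detectable with 80% power moves from the stated 53% to about 61% (uncorrected) or 64% (corrected).

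**Step 4: does Step 3 give the study's power?** It does not, because the answer depends heavily on the clustering factor.

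- *Post-launch months only, same formula for 12 months.* 1 + 11 x 0.15 = 2.65, and 2.65 x 1.276 = 3.381. Effective numbers are 189/3.381 = 55.9 exposed and 378/3.381 = 111.8 controls. Power is 75% without continuity correction.
- *Before-after contrast with controls.* The four cells hold 189 and 378 patients (intervention, after and before) and 378 and 756 (control, after and before). For total design effect T, variance = T x [0.53·0.47/189 + 0.32·0.68 x (1/378 + 1/378 + 1/756)] = T x 0.002757. Replacing 6.25 by an assumed factor of 1.16 to 2.5 gives T = 1.48 to 3.19, SE = 0.064 to 0.094, and power Φ(0.21/SE − 1.96) = 91% down to 61%.
- *The planned model itself.* Generalised least squares for intercept, linear time, quarterly season, QualDash and a hospital random intercept, with only the 3 x 12 post-launch hospital-months exposed. Assumed: a normal approximation, a constant 21-point effect and no phase-in. With a hospital ICC and an additional hospital-month ICC of 0.065 each, power is about 98%; with 0.15 each, about 95%. Adding post-period and group terms gives about 96% and 91%.

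**The case against.** The strongest defence is that the plan's two simplifications pull in opposite directions. Counting pre-launch patients as exposed inflates the sample. Dividing by a 36-month between-hospital design effect deflates it, and that deflation is too severe for a model that compares hospitals with themselves over time. On this view the study may have 80% power or more. This stands as a caution about magnitude: the model-based check in Step 4 gives 91% to 98%. It does not rescue the statement, because one unsuitable factor cannot validate another. The model-based figures also rest on assumed ICCs, a constant effect and no phase-in. Hospital-specific trends, varying effects or a phase-in would lower them.

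One could also read the 71 as an arm label rather than an exposure count. The calculation still compares 71 with 142 as two independent groups, which is not the contrast planned under Analysis.

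A reader might go further and infer from Step 3 that the study is close to a coin toss for the 21-point effect, or that any recalculation must come out worse than 80%. The documents support neither reading. Step 3 applies a factor built for 36 months per hospital to a 12-month block, and the alternatives in Step 4 fall on both sides of 80%.

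**Conclusion.** The exposed count is wrong as written, and the stated 80% power for 32% to 53% does not follow from the plan's inputs. Exposed patients number 189 of 1701, not the 567 behind the effective figure of 71. That conclusion needs only the Protocol's own hospital, month and case counts.

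The size and direction of the effect on power are not settled. With the exposed count corrected and the plan's design effects kept, power is about 44% to 53% (two-sided 0.05 assumed). With clustering factors better suited to a 12-month or within-hospital contrast, it lies anywhere from about 61% to above 90%. The finding is that the power statement is unsupported. It does not show that the study is underpowered.

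**What to change.** In Phase 4, 4a, Sample, replace the 71/142 split with the actual exposure: 189 exposed patients (3 hospitals x 12 months x 5.25) and 1512 unexposed. Recompute power for the QualDash coefficient in the model described under Analysis, treating only post-launch months in the intervention hospitals as exposed. State alpha and sidedness, the ICC assumptions within hospital and within hospital-month, and how any phase-in is handled. Then restate either the power for 32% to 53% or the difference detectable with 80% power, whichever direction it moves.

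The cost is a short recalculation and a protocol wording change. Sites, data collection and the analysis model are unaffected.
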